7.3.3 Adverse events

The following acute adverse events will be evaluated in the glucocorticoid treated patients and patients treated with alternative therapies:

- Composite cardiovascular events (composite of ischemic stroke, haemorrhagic stroke, heart failure, acute myocardial infarction or sudden cardiac death)
- Hypertension
- Arrhythmia
- Gastritis, gastric ulcer, GI bleed
- Psychosis
- Myopathy
- Hyperglycaemia
- Infections
- Any bacterial infection
- Any viral infection
- Any fungal infection
- Any parasitic infection

And if numbers allow, within infections, also separately look at:

- Sepsis
- Lower respiratory tract infections
- Herpes zoster
- Cutaneous cellulitis

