7.3.4 Disease severity outcomes

In ambulatory care cohorts

- Hospital admission
- Venous thromboembolism (VTE) or pulmonary embolism (PE)
- Disseminated intravascular coagulation (DIC)
- Death of any cause

In hospitalized cohorts

- Intensive services as an outcome in inpatient cohorts (including mechanical ventilation and Extracorporeal membrane oxygenation (ECMO))
- Discharge from hospital
- Death of any cause
- Venous thromboembolism (VTE) or pulmonary embolism (PE)
- Disseminated intravascular coagulation (DIC)

They will all be treated as time to event outcomes, see section 7.7 for details.

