SIDIAP is collected from EHR records of patients receiving primary care delivered through Primary Care Teams (PCT), consisting of GPs, nurses and non-clinical staff. The Catalan Health Institute manages 286 out of 370 such PCT with a coverage of 5.6M patients, out of 7.8M people in the Catalan population (74%). The database started to collect data in 2006. The mean follow-up is 10 years. The observation period for a patient can be the start of the database (2006), or when a person is assigned to a Catalan Health Institute primary care centre. Date of exit can be when a person is transferred-out to a primary care centre that does not pertain to the Catalan Health Institute, or date of death, or date of end of follow-up in the database. Drug information is available from prescriptions and from dispensing records in pharmacies. Drugs not prescribed in the GP setting might be underreported; and disease diagnoses made at specialist care settings are not included. Studies using SIDIAP data require previous approval by both a Scientific and an Ethics Committee (9).

Hospital de Madrid (HM) Hospitales (Spain)

Hospital de Madrid (HM) Hospitales data are made available through partnership with SIDIAP. The HM Hospitales database covers in-patient care delivered across a network of private hospitals in Spain. HM Hospitales covers more than 17M patients, out of whom a subset will be catalogued and followed for acute care delivered for suspected COVID-19 onset. This database covers more than 2300 confirmed COVID-19 cases and all in-patient hospital care, including the data of admission, conditions, procedures and medicines dispensed in hospital, date of discharge, and date of known death or date of end of follow-up in the database. Studies using HM Hospitales data require review and approval from data custodians at SIDIAP authorised to execute observational network analyses. The number of newly diagnosed patients in each database per month since the outbreak of COVID-19 can be derived from the databases.

None of the databases, except SIDIAP have linkage between primary and secondary care setting.

A database profiling, describing a range of variables in terms of data quality and completeness, as well as attrition tables for COVID-19 populations can be found at the following link:

https://dqdashboard.iqvia.com/ema_report1/.

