For each sub-cohort and type of person-time the numerator for each time frame will contain the number of patients for whom an outcome has been recorded in that time frame since the onset of that type of person-time. The crude incidence rate of each outcome within the relevant sub-cohort will be expressed as number of cases per 1,000 patient-days at risk.

The cumulative incidence rate will be reported at the end of follow-up (30 and 90 days).

The person-time estimation and the calculation of the crude incidence rate for secondary objectives 2 and 3 will be similar except for the outcomes being considered in each case. For secondary objective 2, adverse events of interest for glucocorticoids (listed in Section 7.3.3) will be the outcome, and for secondary objective 3 mortality and other disease outcomes (Section 7.3.4) will be the outcome.

Both stratification and adjustment will be used as a method to deal with confounders.

In order to examine risk factors of the outcomes of interest, data will also be stratified by subgroups of interest (7.2.4) and stratum-specific crude incidence rates will be calculated. The stratification variables include the healthcare setting, glucocorticoid user type (naive, prevalent) treatment groups and subgroups of special interest.

Separate Cox regression models will be used to estimate adjusted cause-specific HR³ (in order to account for competing events) for each outcome **within** the following four treatment groups:

- Use of systemic glucocorticoids without other treatments for COVID-19 (drug and respiratory support)
- Use of systemic glucocorticoids plus other treatments for COVID-19 (drug and respiratory support)
- Only other treatments and respiratory support with no systemic glucocorticoids

³ Cause-specific HR are to be interpreted as instantaneous risk estimates and not as cumulative risk estimates; cumulative risks estimates are subject to competing events <https://pubmed.ncbi.nlm.nih.gov/30012114/>

- No specific treatments for COVID-19 infection (other concomitant treatments for indications other than for COVID-19 are allowed)

In addition to stratified analysis, for each of the above four treatment groups, two sets of Cox regression models will be run:

- 1) A model that is adjusted for a list of predefined confounders
- 2) A model that is adjusted for a high dimension propensity score that is derived through large-scale modelling, using all available covariates in each dataset (Section 7.7.5)

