3.5. Gastrointestinal bleeding

Concept ID	Concept name
4147683	Acute gastrojejunal ulcer without hemorrhage AND without perforation
40482685	Angiodysplasia of duodenum
28779	Bleeding esophageal varices
198798	Dieulafoy's vascular malformation
4198381	Ulcer of duodenum
4112183	Esophageal varices with bleeding, associated with another disorder
4265600	Gastric ulcer
192671	Gastrointestinal hemorrhage
4027663	Peptic ulcer

3.6. Composite cardiovascular disease events (ischemic stroke, hemorrhagic stroke, heart failure, acute myocardial infarction or sudden cardiac death)

Concept ID	Concept name
4329847	Myocardial infarction
316139	Heart failure
376713	Cerebral hemorrhage
439847	Intracranial hemorrhage
43530674	Spontaneous cerebellar hemorrhage
43530727	Spontaneous cerebral hemorrhage
42535425	Spontaneous hemorrhage of cerebral hemisphere
4148906	Spontaneous subarachnoid hemorrhage
432923	Subarachnoid hemorrhage
372924	Cerebral artery occlusion
375557	Cerebral embolism

443454	Cerebral infarction
441874	Cerebral thrombosis
4048809	Brainstem death
321042	Cardiac arrest
442289	Death in less than 24 hours from onset of symptoms
4317150	Sudden cardiac death
4132309	Sudden death

4. Disease outcomes

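### Code list 3.6 does not match the cardiovascular composite in Section 7.3.3: it can count non-cardiac deaths as events and can miss strokes recorded without a subtype

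*Protocol*

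**What the plan says.** Section 7.3.3 of the protocol defines the composite cardiovascular event as a "composite of ischemic stroke, haemorrhagic stroke, heart failure, acute myocardial infarction or sudden cardiac death". The heading of list 3.6 in Appendix 1 repeats the same five components. Eighteen concepts stand under that heading. Five concern death or arrest: Brainstem death, Cardiac arrest, "Death in less than 24 hours from onset of symptoms", Sudden cardiac death and Sudden death. Eleven concern stroke, among them "Cerebral infarction" and "Intracranial hemorrhage".

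Section 7.7.4 analyses each outcome with cause-specific Cox models "in order to account for competing events", and Section 7.2.3 lists death as a reason for censoring. "Death of any cause" is a separate outcome in Section 7.3.4, with its own concept in list 4.7.

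Appendix 1 is titled as an example of code lists, but its introduction says that the concepts are the ones used to define each indication or risk group. Section 7.3 says that variables will be identified with pre-specified, expert-reviewed concept sets.

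**The concern.** A code list is the working definition of an outcome, so it should capture the events that the text names and no others. List 3.6 departs from the text in two ways.

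The more important one concerns deaths. The text admits one kind of death, the sudden cardiac kind. The list admits three more concepts that say nothing about the heart. In a COVID-19 cohort many deaths are respiratory. If such a death carries one of these codes, it moves from the competing events into the event of interest. Section 7.9.1 says that glucocorticoids are indicated in severe cases only. Deaths are likely to be more frequent in such patients, so the composite rate in the steroid groups could partly reflect COVID-19 mortality and be read as cardiovascular harm. The composite is one of the outcomes named in secondary objective 2 (Section 6.3).

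The second concerns stroke. The composite takes ischaemic and haemorrhagic stroke alike, so the subtype does not matter for membership. A stroke recorded only without a subtype nevertheless matches none of the listed concepts.

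**Working it through.** The protocol gives no event rate or precision figure for this outcome, so there is no stated number to reproduce. The check is a comparison of the list with the definition, followed by an illustration of scale.

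**1. The 18 concepts against the five components**

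| Component in Section 7.3.3 | Concepts in list 3.6 | Number |
|---|---|---|
| Acute myocardial infarction | 4329847 | 1 |
| Heart failure | 316139 | 1 |
| Haemorrhagic stroke | 376713, 439847, 43530674, 43530727, 42535425, 4148906, 432923 | 7 |
| Ischaemic stroke | 372924, 375557, 443454, 441874 | 4 |
| Sudden cardiac death | 4317150 | 1 |
| Arrest, cause of death not stated | 321042 Cardiac arrest | 1 |
| No matching component | 4048809 Brainstem death; 442289 death within 24 hours of symptoms; 4132309 Sudden death | 3 |

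Total: 1 + 1 + 7 + 4 + 1 + 1 + 3 = 18.

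**2. Deaths.** Concept 4317150 already covers the component that the text names. The three concepts in the last row carry no cardiac restriction, and no rule elsewhere in the protocol removes COVID-19 deaths from the composite. In a cause-specific model a non-cardiac death should end follow-up as a competing event. With list 3.6 as printed, the same death is an event if it carries one of the three codes. Cardiac arrest is a different case: it names the heart, but it can be recorded at a death from another cause, so it calls for a sensitivity comparison rather than deletion.

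**3. Stroke.** The stroke concepts number 7 + 4 = 11. Each names a haemorrhage, or an occlusion, embolism, infarction or thrombosis. None is a general stroke or cerebrovascular accident concept. The list does not say whether descendants are included, but including them would not help here, because a general concept is not a descendant of a more specific one.

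**4. Scale, for illustration only.**

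- Hospital patients: about 2,000 (Section 7.5).
- Case fatality: 26%. Section 5.0 gives over 26% for UK hospital admissions; applying it to this cohort is an assumption.
- Deaths: 2,000 × 0.26 = 520.
- Share of deaths carrying one of the three codes: not in the documents, assumed 1% to 10%.

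| Assumed share | Deaths entering the composite | As a proportion of 2,000 patients |
|---|---|---|
| 1% | 520 × 0.01 = 5.2 | 0.26% |
| 5% | 520 × 0.05 = 26 | 1.3% |
| 10% | 520 × 0.10 = 52 | 2.6% |

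These are deaths that would enter whatever their cause; some could be truly cardiac. The documents give no true composite incidence, so relative inflation cannot be calculated. Nor can the number of missed strokes, because neither a stroke rate nor the share recorded without a subtype is given.

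**The case against.** The strongest reply is that the list is only an example and that final concept sets may stand in the statistical analysis plan. This lowers the weight of the point but does not remove it. The same introduction says that the concepts are used in the definitions, and the protocol prints no other operational definition of the composite.

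It can also be said that the death codes may be rare. The hospital source records admission, discharge and known death dates (Section 7.4), and nothing shows that deaths there also receive condition codes. A patient who dies many days after COVID-19 symptoms began does not obviously fit the 24-hour concept. The hospital cohorts leave out patients with intensive services in the 30 days before or on index (Section 7.2.2), and follow-up for objectives 2 and 3 is on treatment and censored at switching (Section 7.3.2.3), so 520 deaths may be too many. All of this bears on size, which is unknown, and not on the mismatch itself.

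On stroke, the 11 concepts do match the two named subtypes, and leaving out an unspecified code can be defended as a choice for specificity. That is fair, and it is why stroke is the secondary part. The limit on SIDIAP, that "disease diagnoses made at specialist care settings are not included", does not strengthen this part: a diagnosis that is absent from the database cannot be recovered by adding a code.

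Finally, the study is non-comparative (Sections 6.3 and 7.9.1) and warns about confounding by severity. That warning concerns who is treated; it does not cover an outcome that contains deaths outside its own definition.

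**Conclusion.** The point holds as a mismatch between definition and code list. Three death concepts go beyond sudden cardiac death, so non-cardiac deaths that carry one of them can be counted as cardiovascular adverse events. The stroke gap is real on the page but secondary. The figure of 5 to 52 hospital deaths depends on a UK fatality figure and an assumed 1% to 10% coding share, and shows only that the effect need not be negligible.

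A reader might infer more than the documents support:

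- That COVID-19 deaths in general become cardiovascular events. Only those recorded with one of the listed codes do.
- That strokes coded in general practice are missed. The documents do not say how general practitioners code stroke, and strokes coded as infarction or haemorrhage are captured.
- That the errors run in opposite directions in hospital and ambulatory data. The same list applies in both settings, and either error can occur in either.
- That counting one death under both objective 2 and objective 3 is itself a fault. The outcomes are analysed separately, and a true sudden cardiac death also counts in both. The fault is the wrong cause.

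**What to change.** Reconcile list 3.6 with Section 7.3.3 before extraction, which Section 7.2.1 sets for 1 February 2021 at the latest:

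- Remove 4048809, 442289 and 4132309 from the main composite, or move them to a sensitivity definition.
- Keep 4317150 Sudden cardiac death.
- Report the composite with and without 321042 Cardiac arrest.
- Add a concept for stroke of unspecified type, or state why it is left out.
- State that all other deaths are competing events for this outcome, and whether descendant concepts are included.

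The cost is a few edits to the list and an extra row in the outcome tables. The downside is small: some true sudden cardiac deaths coded only as Sudden death leave the main composite. They remain in all-cause death only where vital status is recorded, and Section 7.9.2 says that DA Germany, LPD France and LPD Italy do not record it. A sensitivity definition that keeps the three concepts would show how many such records there are.

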4.1. Hospital admission

Concept ID	Concept name
262	Emergency Room and Inpatient Visit
9201	Inpatient Visit

4.2. Hospital discharge

Concept ID	Concept name
4203130	Discharge from hospital

4.3. Intensive services

Concept ID	Concept name
4338595	Cardiac support using extracorporeal membrane oxygenation circuitry
4052536	Extracorporeal membrane oxygenation
44811012	Fluoroscopy guided percutaneous insertion of cannula for extracorporeal membrane oxygenation
4230167	Artificial respiration
40481547	Dependence on ventilator
4080957	Endotracheal respiratory assistance
4168966	Endotracheal tube present
4232550	Home visit for mechanical ventilation care
4235361	Hyperventilation therapy for traumatic brain injury
37116689	Insertion of endotracheal ventilation catheter
40487536	Intubation of respiratory tract
4332501	Management of noninvasive mechanical ventilation
37206832	Mechanical insufflation exsufflation
765576	Orotracheal intubation using bougie device
4219858	Problem with patient ventilator
4237618	Ventilator care
4251737	Ventilator care management

44791135	Ventilatory support
4072633	Weaning from mechanically assisted ventilation
4166281	Anterior tracheostomy
4115488	Emergency tracheostomy
4337047	Insertion of tracheostomy tube
4168864	Lateral tracheostomy
4199580	Mediastinal tracheostomy
4065590	Permanent tracheostomy
4311023	Revision of stoma of trachea
4195473	Temporary tracheostomy
4208093	Tracheostomy, emergency procedure by transtracheal approach
262	Emergency Room and Inpatient Visit
9201	Inpatient Visit

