7.2.2 Patient Selection

7.2.2.1 Inclusion Criteria

Four cohorts will be created based on healthcare setting and type of steroid use. Their eligibility criteria being described below (using Covid-19 catch-all definition Section 7.3.1):

Ambulatory prevalent user

- Have at least 365 days of continuous observation time prior to cohort entry
- Have a glucocorticoid (oral or parenteral) exposure in the 120 days prior to diagnosis date (unrelated to COVID-19 diagnosis)
- Have a positive PCR test for SARS-CoV-2 (labCOVID-19) or a confirmed COVID-19 diagnosis (diagCOVID-19)
- Have no hospitalizations in the 30 days prior to or on index

Ambulatory naive user

- Have at least 365 days of continuous observation time prior to cohort entry
- Have no glucocorticoid (oral or parenteral) exposure in the 120 days prior to index (unrelated to COVID-19 diagnosis)
- Have a positive PCR test for SARS-CoV-2 (labCOVID-19) or a confirmed COVID-19 diagnosis (diagCOVID-19)
- Have no hospitalizations in the 30 days prior to or on index

Hospitalized prevalent user

- Have a glucocorticoid (oral or parenteral) exposure in the 120 days prior to index (unrelated to COVID-19 diagnosis)
- Have a positive PCR test for SARS-CoV-2 (labCOVID-19) or a confirmed COVID-19 diagnosis (diagCOVID-19) (index date)
- Are hospitalized 30 days prior or after diagnosis index date
- Have no intensive services in the 30 days prior to or on index

Hospitalized naïve user

- Have no prior exposures to glucocorticoids in the 120 days prior to index
- Have a positive PCR test for SARS-CoV-2 (labCOVID-19) or a confirmed COVID-19 diagnosis (diagCOVID-19)
- Are hospitalized 30 days prior or after diagnosis index date
- Have no intensive services in the 30 days prior to or on index

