4.4. Invasive mechanical ventilation

Concept ID	Concept name
4230167	Artificial respiration
40481547	Dependence on ventilator
4080957	Endotracheal respiratory assistance
4168966	Endotracheal tube present
4232550	Home visit for mechanical ventilation care
4235361	Hyperventilation therapy for traumatic brain injury
37116689	Insertion of endotracheal ventilation catheter
40487536	Intubation of respiratory tract
4332501	Management of noninvasive mechanical ventilation
37206832	Mechanical insufflation exsufflation
765576	Orotracheal intubation using bougie device
4219858	Problem with patient ventilator
2788037	Respiratory Ventilation, 24-96 Consecutive Hours
2788038	Respiratory Ventilation, Greater than 96 Consecutive Hours
2788036	Respiratory Ventilation, Less than 24 Consecutive Hours
4237618	Ventilator care
4251737	Ventilator care management
44791135	Ventilatory support
4072633	Weaning from mechanically assisted ventilation

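### The concept list for intensive services contains the two generic admission concepts, so as printed it excludes hospital patients admitted on or before diagnosis and counts ordinary later admissions as the severity outcome

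*Protocol*

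**What the plan says.** **Cohort entry.** Protocol Section 7.2.2.1 sets two criteria for both hospital cohorts, prevalent and naïve: "Are hospitalized 30 days prior or after diagnosis index date" and "Have no intensive services in the 30 days prior to or on index".

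**Outcome.** Section 7.3.4 lists "Intensive services as an outcome in inpatient cohorts" among the disease severity outcomes and describes it as including mechanical ventilation and ECMO.

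**Concept list.** Appendix 1, list 4.3 (Intensive services), holds 30 concepts. The last two are 262, "Emergency Room and Inpatient Visit", and 9201, "Inpatient Visit". List 4.1 (Hospital admission) consists of these same two and nothing else.

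**Status of the lists.** The heading of Appendix 1 presents them as examples. Its opening sentence says they define the indications and risk groups, and Section 7.3 says variables are identified from concept sets fixed in advance.

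**Data source.** Section 7.5 states that only one database observes hospitalised patients, around 2,000 of them. Section 7.4 describes that source, HM Hospitales, as covering in-patient care.

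**The concern.** The same two concepts define being admitted and, as printed, also qualify a patient as having received intensive services. A hospital cohort cannot sensibly require the first and forbid the second when one record satisfies both. A programmer who builds the cohort from the printed list would discard patients because they were in hospital, which is the condition that puts them in the cohort.

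Two results are at stake. The hospital half of the primary objective rests on a single source of about 2,000 patients, and an unknown part of it would be lost at entry. The intensive-services outcome under secondary objective 3 is meant to capture escalation to ventilation or ECMO. It would instead mix such escalation with ordinary admissions.

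**Working it through.** **Step 1. Compare the lists.**

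- List 4.3 has 3 ECMO concepts, 16 ventilation concepts, 9 tracheostomy concepts and 2 visit concepts: 3 + 16 + 9 + 2 = 30.
- Removing the ECMO, ventilation and tracheostomy concepts leaves exactly 262 and 9201, which is list 4.1 in full.
- The related lists 4.4 (Invasive mechanical ventilation), 4.5 (ECMO) and 6.2 (Invasive respiratory support) contain neither visit concept.
- All 28 clinical concepts of list 4.3 are in list 6.2, which has one more (2743216).

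**Step 2. Look for a combining rule.** Nothing in Section 7.2.2.1, Section 7.3.4 or Appendix 1 says that a visit concept counts only with a procedure, an intensive-care stay or another qualifier.

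**Step 3. Apply both entry criteria by day of admission, taking any listed concept as intensive services.**

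- Hospitalised within 30 days either side of index: days -30 to +30, so 30 + 1 + 30 = 61 admission days qualify.
- No intensive services before or on index: days -30 to 0 are removed, which is 30 + 1 = 31 days.
- Left: 61 - 31 = 30 days, namely first admissions on days +1 to +30.

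**Step 4. Size of the loss.** Let f be the share of hospital patients admitted on or before index. The protocol does not give f, so the values below are assumptions. Patients left = 2,000 × (1 - f).

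| Assumed f | Patients left |
|---|---|
| 0.50 | 1,000 |
| 0.70 | 600 |
| 0.90 | 200 |
| 0.95 | 100 |
| 1.00 | 0 |

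Because the source holds in-patient care, a high f is plausible, but the protocol does not establish it.

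**Step 5. The outcome.** Under Sections 6.3, 7.1 and 7.2.3, outcome follow-up runs from the treatment index date. Hospital discharge is not among the censoring criteria in Section 7.2.3, so a readmission can fall within follow-up. With 262 and 9201 in the list, any inpatient visit starting after that date meets the outcome.

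**Step 6. With the two concepts removed.** List 4.3 falls from 30 to 28 concepts, and an admission on any of the 61 days is compatible with both entry criteria.

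**Step 7. Two neighbouring lists.** Concept 4332501, "Management of noninvasive mechanical ventilation", sits in lists 4.4 and 6.2, both headed as invasive. List 5.7 (Obesity) includes a plain body-weight concept, whereas Section 7.3.5 bases obesity on diagnosis codes.

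**The case against.** The best defence is that Appendix 1 gives examples and prints concept identifiers without cohort logic. Some lists plainly need logic held elsewhere: list 1.3 mixes detected and not-detected test results, and the fever list includes temperature measurements with no threshold. The visit concepts in list 4.3 could likewise be a co-condition, meaning a procedure during an inpatient stay. Section 7.3 promises expert review of the concept sets, and the exclusion summary in Section 7.7.1 would reveal a large loss. This shows that the literal reading is not the only one. It does not settle the matter, because the appendix says the concepts are used for the definitions and the co-condition is written nowhere.

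A reader might also infer more than the protocol supports:

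- **That the outcome is 100% by construction.** Follow-up starts at the treatment index date, so an admission between diagnosis and treatment start is not a follow-up event. Section 7.2.3 ties that date to a glucocorticoid start and leaves it undated for the groups without glucocorticoids, but that gap does not support a blanket figure either.
- **That the hospital cohort is nearly emptied.** This depends on f, which is not given.
- **That ulcer concepts such as "Acute gastrojejunal ulcer without hemorrhage AND without perforation" should leave list 3.5.** Section 7.3.3 groups gastritis, gastric ulcer and GI bleed in one outcome, and Appendix 1 has no other ulcer list. Cutting these concepts would strip out part of a named outcome. At most the heading of list 3.5 is too narrow.
- **That list 5.8 flags non-smokers as smokers.** Holding both statuses is consistent with a status variable, as in list 1.3.
- **That the entry criterion belongs elsewhere.** Excluding patients with intensive services on or before index parallels the no-hospitalisation criterion in the ambulatory cohorts. It leaves in those ventilated later. Its placement is a design trade-off, not an error.

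**Conclusion.** The point holds for list 4.3. As printed, the list conflicts with the cohorts in Section 7.2.2.1 and blurs the outcome in Section 7.3.4. Patients admitted on days -30 to 0 would be excluded, and those first admitted on days +1 to +30 would stay. The loss runs from about half to all of the roughly 2,000 hospital patients, on the assumption that 50% to 100% were admitted on or before index. Intensive services during follow-up could not be told apart from an ordinary admission. Both consequences rest on reading any listed concept as sufficient, which is the only reading the protocol states. The noninvasive ventilation concept and the body-weight concept are smaller inconsistencies of the same kind.

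**What to change.** Before extraction:

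1. Delete 262 and 9201 from list 4.3, or state that they count only together with a listed ventilation, tracheostomy or ECMO concept. Check the result against Sections 7.2.2.1 and 7.3.4.
2. Take 4332501 out of lists 4.4 and 6.2.
3. Reconcile the body-weight concept in list 5.7 with the diagnosis-code definition of obesity in Section 7.3.5.

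Leave the ulcer concepts in list 3.5, list 5.8 and the position of the entry criterion as they are. The cost is a few edits to concept sets, or one sentence of combining logic. No new data and no change to the design are needed.
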